## **13.6 Adverse Event Follow-up**

All treatment-related AEs must be followed in accordance with the International Conference of Harmonization (ICH) Good Clinical Practice (GCP) guidelines, and other applicable regulatory

requirements (e.g., US Code of Federal Regulations [CFR] 812). The expected AE of mild hematoma (bruise) and/or mild infiltration are not followed to resolution.

## **13.7 Serious Adverse Events and Unanticipated Adverse Device Effect**

### **13.7.1 Definition**

In the interest of subject care and to allow Terumo BCT to fulfill all regulatory requirements, any SAE and/or UADE, regardless of causal relationship to study treatment/procedure(s), must be reported to Terumo BCT within 24 hours of knowledge of the event.

SAEs are defined (21 CFR 312.32 and ISO 14155:2011 Sec. 3.37) as those AEs which meet any of the following criteria:

- Results in death
- Led to serious deterioration in the health of the subject, that either resulted in
- A life-threatening illness or injury, or
- A permanent impairment of a body structure or a body function, or
- Inpatient or prolonged hospitalization, or
- Medical or surgical intervention to prevent life-threatening illness or injury or permanent impairment to a body structure or a body function.
- Led to fetal distress, fetal death or a congenital abnormality or birth defect.

NOTE: Planned hospitalization for a pre-existing condition or a planned procedure, without serious deterioration in health, is not considered a serious adverse event.

Unanticipated adverse device effect (UADE): per 21 CFR 812.3 a UADE is defined as any serious adverse effect on health or safety or any life-threatening problem or death caused by, or associated with a device, if that effect, problem or death was not previously identified in nature, severity, or degree of incidence in the CIP and/or Trima Accel operators manual, or any other unanticipated serious problem associated with a device that relates to the rights, safety, or welfare of subjects.

NOTE: Anticipated adverse device effects are effects, which by nature, incidence, severity or outcome have been identified in the CIP and/or Trima Accel operators manual.

### **13.7.2 SAE/UADE Reporting**

Any AE/SAE/UADE that occurs after signing the ICF until study completion/termination must be reported. Follow-up (regardless of relationship to the study treatment/procedure[s]) must be reported and an AE/SAE/UADE Form must be submitted to Terumo BCT within 24 hours of knowledge of the event to:

Terumo BCT  
Email: [[contact]](mailto:[contact])  
[contact]

Terumo may request additional information from the Investigator to ensure the timely completion of accurate safety reports.

Additionally the SAE/UADE must be entered on the AE page(s) of the CRF. Follow-up SAE/UADE reports need to be submitted to Terumo BCT as soon as additional information regarding the event becomes available.

Terumo BCT will be responsible for reporting SAE/UADEs to the regulatory authorities in accordance with applicable regulatory reporting guidelines. The Investigator is responsible for submitting SAE/UADEs to his/her Institutional Review Board (IRB) as required by local policy.

#### **Exclusions to SAE/UADE Reporting Requirements**

The following are not considered SAEs/UADEs:

- Planned hospitalization.
- Anticipated day-to-day fluctuations of pre-existing condition(s) present or detected at the start of the study that do not worsen.

### **13.8 Clinical Investigation Plan Deviations**

A CIP deviation is defined as any event where the Investigator or site personnel deviate from the study CIP or study procedures for any reason.

All CIP deviations will be reported to the Sponsor. Protocol deviations that may affect the scientific soundness of the study or affect the rights, safety, or welfare of study subjects, must be reported to the Sponsor and the IRB as per the IRB's standard reporting procedure.

## **13.9 Medical Monitoring**

It is the responsibility of the PI to oversee the safety of the study at his/her site. There will not be a Data Safety Monitoring Board for this study because it involves healthy subjects undergoing a commonly practiced research evaluation procedure.

Terumo BCT will monitor the safety of the study subjects on an ongoing basis.

## **14 STUDY DEVICE**

### **14.1 Device Deficiencies**

All device deficiencies involving any device component must be reported within 24 hours upon knowledge to the Sponsor utilizing the Device Deficiency Report Form. Every attempt should be made by the Site to save or collect the defective device, and if appropriate, the packaging, for return to the Sponsor. A qualified company representative will investigate and determine root cause and corrective actions as applicable, and directives will be provided to the site if warranted.

### **14.2 Device Accountability**

#### **14.2.1 Receipt of Study Device**

The contents should be examined upon receipt to ensure packaging and labeling is intact and the devices have not been damaged. Any damage should be immediately reported to the Sponsor.

#### **14.2.2 Storage**

The device and disposables should be stored in a dry place at room temperature. Proper care should be taken to ensure that the study inventory will not be damaged.

#### **14.2.3 Accountability**

The Trima Accel device, disposables, arm cuff and software will be provided by Terumo BCT for use in this study. The Trima Accel disposables are FDA cleared and marketed in the United States.

## **15 STATISTICAL PLAN**

The following section summarizes the statistical methods that will be used in the analysis of the clinical data from this active-controlled trial. Continuous variables will be described using means, medians, and measures of dispersion including standard deviation and ranges with categorical variables will be summarized with frequencies and percentages.

## **15.1 Sample Size**

As specified in the FDA guidance, for up to 1 allowed failure, 93 platelet products are required to show that the proportion of platelet units with an acceptable residual WBC level is at least 95% with 95% confidence. With 93 platelet products being collected, 16 failures or less is required to show that the proportion of platelet units with an acceptable platelet yield is at least 75% with 95% confidence.

## **15.2 Outcome Measures**

### **15.2.1 Primary Endpoint**

The primary endpoint for this study is the proportion of platelet units with an acceptable residual WBC level. Counts and percentages of success rates and the lower one-sided 95% exact binomial confidence intervals will be calculated separately for success rates of single, double, and triple platelet products. If 0 or 1 failure is observed, then the confidence interval will suggest that the true success rate is at least 95% with 95% confidence for the given platelet product. This approach will be applied independently to single, double, and triple platelet products.

### **15.2.2 Secondary Endpoint**

The secondary endpoint of platelet yield will be summarized for single, double, and triple platelet products. Separately for single, double, and triple platelet products, the lower one-sided 95% exact binomial confidence intervals will be calculated for the proportion of platelet units with an acceptable platelet yield. If 16 or fewer failures are observed, then the confidence interval will suggest that the true success rate is at least 75% with 95% confidence for the given platelet product.

### **15.2.3 Safety Measures**

Adverse events will be summarized by the medical dictionary for regulatory activities (MedDRA Version 18.1 or later). Tables will describe the frequency and percentage of all AEs, SAEs, and UADEs reported by subjects in the safety population. Presentations will summarize AEs by maximum reported severity and relationship to device and procedure. AEs leading to study or procedure discontinuation will also be tabulated.

## **15.3 Analysis Populations**

The safety population will include of all subjects enrolled in this trial for whom at least 1 apheresis procedure is initiated. The Full Analysis Set (FAS) will be defined separately for single, double, and triple platelet products. The FAS for a given platelet product will consist of the first 93 collections that do not meet any of the protocol exclusion criteria described in Section 15.4. The FAS will be used to examine the primary and secondary endpoints.

## 15.4 Protocol Analysis Exclusions

Data points will be excluded from analysis in the following situations:

1. Inability to collect a complete unit due to:
  - a. Subject issues (inadequate access, reaction, needle abort, procedure disqualification upon Trima Accel device update of subject platelet count and hemoglobin or hematocrit).
  - b. Decision to stop procedure by subject, Investigator, nursing staff or operator.
  - c. Equipment failure or malfunction (unrecoverable system failure; plugged or malfunctioning filter[s]).
  - d. Protocol deviation.
2. Decision to stop the procedure due to a change in the subject platelet count (ie subject qualifies for double, however day-of platelet count is for a single platelet product and 93 single platelet products have already been collected).
3. Failure or inability to update the Trima Accel system with the actual platelet count (platelet count performed on sample taken from Trima Disposable sample pouch) AND the actual platelet count differs from the entered platelet count by more than 10%. Updating the Trima Accel system with actual platelet count from the sample pouch is standard procedure for the Trima Accel system.
4. Incomplete or incorrect collection procedure or post-collection processing due to:
  - a. Equipment failure or malfunction.
  - b. Subject issues (inadequate access, reaction, needle abort).
  - c. Unanticipated centrifuge stop during collection procedure.
  - d. Failure to follow collection or post-collection handling procedure outlined in the Trima Operator's Manual, and supplement(s).
  - e. Subject and procedure samples are not taken as specified in protocol.
  - f. Incorrect solution added to platelets prior to storage (eg platelet additive solution).
  - g. Results of endpoint assays are not available.

## **16 STUDY MANAGEMENT**

### **16.1 Investigator Responsibilities**

#### **16.1.1 Investigator Agreement**

Each Investigator will provide the Sponsor a copy of his/her current curriculum vitae and a signed Investigator Agreement, prior to initiation of the study.

#### **16.1.2 Institutional Review Board**

The IRB or other committee functioning in a similar capacity will review and approve the protocol and any protocol amendments, initial and revised informed consent (IC) documents, and recruitment materials, if applicable. After approval by the IRB, documentation of approval and the approved IC document will be sent to Terumo BCT before any subject is enrolled into this study.

#### **16.1.3 Informed Consent**

The Investigator is responsible for preparing the written IC document for this study. Terumo BCT will provide the Investigator an IC template. The Investigator may rearrange or reword the contents of the template, or may add other elements or language, provided the meaning and content are not changed or deleted.

Prior to subject participation in this study, the Investigator must obtain written IRB approval for the protocol and the ICF. The approved consent form will clearly reflect the IRB approval date.

Once the subject's initial eligibility has been determined, the Investigator or person designated by the Investigator, who has been trained on the protocol, will explain the nature and scope of the study, potential risks and benefits of participation, answer questions for the subject and ask the subject to participate in the study. The study will be explained to the study subject in lay terms, in their native language in a quiet, non-disruptive setting. Potential subjects will be given as much time and privacy as necessary to review the informed consent prior to agreeing to participate in the study. Additionally, if the subject desires, they can take a copy of the consent with them so that they can discuss potential participation with others outside the study team. If the subject agrees to participate, the subject has read the ICF, and has had all of their questions answered, then the ICF must be signed and personally dated by the subject and the person completing the consent process. A copy of the signed and dated ICF will be provided to the study subject.

All subjects are free to withdraw from participation in this study at any time, for any reason(s), specified or unspecified, and without prejudice. The reason(s) for the subject discontinuing or terminating from the study must be recorded on the eCRF.

#### **16.1.4 Study Files and Record Retention**

Investigational sites will maintain all records pertaining to this study for a minimum of 2 years following pre-market approval or 2 years after the study is discontinued. The sponsor will notify investigational sites of the discontinuation. Prior to discarding any study-related records, all clinical sites must contact the sponsor for direction.

#### **16.1.5 Regulatory Compliance**

Sites are responsible for meeting all applicable FDA regulations (eg, 21 CFR 600-680 and 21 CFR 800) and AABB standards. Sites will be responsible for staying current on new standards and meeting any new regulations which may be implemented during the course of this study.

### **16.2 Sponsor Responsibilities**

#### **16.2.1 Amendments to the Clinical Investigation Plan**

Any amendment to the protocol, as deemed appropriate by Terumo BCT, will be implemented as the study progresses. Amendments will be submitted to the IRB for written approval, before implementation.

#### **16.2.2 General Responsibilities**

As per ISO 14155 Section 8 and 21 CFR 812, Terumo BCT is responsible for selecting qualified Investigators and providing them with the information they need to conduct the investigation properly, ensuring quality study conduct and proper monitoring of the investigation, ensuring required approvals are obtained and that significant new information about an investigation is promptly reported to reviewing IRB/EC and government authorities as well as annual reports as required.

### **16.3 Joint Investigator-Sponsor Responsibilities**

#### **16.3.1 Training**

The Sponsor will train applicable study team members as to the device, protocol, and study procedures and will provide updated information as it becomes available during the course of the study, if applicable. The Investigator is responsible for ensuring that additional site personnel that were not trained by the Sponsor receive applicable documents and training.

### **16.4 Collecting and Recording Data**

The Investigators will maintain complete, accurate, legible, and easily retrievable data, and will allow personnel authorized by Terumo BCT access to all study data at any time. Such data shall also be secured in order to prevent loss of data.

All required data for this study will be recorded from the source documentation onto standardized eCRFs.

#### **16.4.1 Source Documents**

Source data is all information, original records of clinical observations, or other activities in a clinical trial necessary for the reconstruction and evaluation of that trial. Source data are contained in source documents. Examples of these original documents and data records include Blood Center records, evaluation checklists, and laboratory results.

#### **16.4.2 Case Report Forms**

The study eCRF via EDC is the primary data collection instrument for the study. All data must be recorded in English. Any missing data must be explained.

Completed eCRFs will be reviewed and signed by the Investigator. The CRA will verify the EDC data with the subject's source data, evaluate the data for accuracy, consistency, and completeness, and will ensure that all forms with missing data and/or errors are ultimately addressed. Accurate and complete eCRFs for a subject must be completed in a timely manner.

### **16.5 Protocol Compliance**

The Investigator is responsible for ensuring the study is conducted in accordance with the procedures and evaluations described in this protocol

### **16.6 Termination of the Study**

For reasonable cause, either the Investigator or the Sponsor may terminate the Investigator's participation in this study, provided a written notice is submitted within the time period provided for in the Clinical Trial Agreement (CTA). In addition, Terumo BCT may terminate the study at any time upon immediate notice for any reason, including but not limited to, Terumo BCT's belief that termination is necessary for the safety of subjects or failure to meet the primary endpoints.

### **16.7 Publication Policy**

Terumo BCT recognizes the importance of communication of medical study data, and encourages the publication of such data in reputable scientific journals and the presentation of such data at scientific seminars and conferences. Any proposed publication or presentation of the data generated from the study must be provided to Terumo BCT for timely review in accordance with the terms of the CTA between the Investigator, the Institution, and Terumo BCT. Terumo BCT shall not, in its scientific publications or promotional material, quote from publications by Investigators without full acknowledgment of the source. As this will be a multi-site study, all

Investigators agree not to publish individual site data. All study data will be published as 1 or more manuscripts based on the accumulated data from all study sites.

1.0 Introduction

This statistical analysis plan (SAP) is being developed after review of the protocol CTS-5060 and electronic case report forms (eCRFs). Reference materials for this SAP include the Clinical Investigation Plan (CIP) and the eCRFs.

The purpose of this plan is to prospectively (a priori) outline the types of analyses and presentations of data that will form the basis for conclusions to be reached that will answer the study objectives outlined in the CIP. This plan explains in detail how the data will be handled or analyzed, adhering to commonly accepted standards and practices of biostatistical analysis in the medical device industry.

The overall objective of this study will be achieved through descriptive analyses involving the device efficiency and safety variables collected in this study. All variables will be reported in listing format. All variables specified in this SAP will be analyzed and presented in descriptive tabulations and selected variables will be summarized and compared with criteria in FDA Guidance for Industry on Collection of Platelets by Automated Methods. The study objectives will be explored through the pre-specified primary, secondary, and safety endpoints.

This document contains information to support the generation of a Clinical Investigation Report (CIR) for Clinical Protocol CTS-5060, including detailed descriptions of the statistical methodologies to be applied, as well as the in-text tables, analysis summary tables, subject data listings, and descriptive graphics intended to present the analysis results.

The planned analyses identified in this SAP may be included in regulatory submissions and/or future manuscripts. Exploratory analyses, not identified in this SAP, may be performed to support the clinical development program. Any post-hoc, or unplanned, analyses that are performed but not identified in this SAP will be clearly identified in the CIR. The structure and content of this SAP provides sufficient detail to meet the requirements identified by the FDA and International Conference on Harmonisation of Technical Requirements for Registration of Pharmaceuticals for Human Use (ICH): Guidance on Statistical Principles in Clinical Trials.

2.0 Study Objectives

The objective of this study is to verify that platelets collected on the Trima Accel System, Version 7.0 and stored in 100% plasma meet the FDA requirements for leukoreduction.

3.0 Statistical Methodology

All statistical analyses will be performed using SAS[®] software version 9.3. All testing and/or confidence intervals will be at a significance level of 0.05 unless stated otherwise.

3.1 Sample Size

As specified in the FDA guidance, for up to 1 allowed failure, 93 platelet products are required to show that the proportion of platelet units with an acceptable residual WBC level is at least 95% with 95% confidence. With 93 platelet products being collected, 16 failures or less is required to show that the proportion of platelet units with an acceptable platelet yield is at least 75% with 95% confidence.

Up to 450 healthy adult subjects will be enrolled in this study to complete 279 procedures (93 single, 93 double, and 93 triple platelet products).

3.2 Study Populations

Analysis populations for this clinical investigation will be the Full Analysis Set (FAS) and Safety Populations.

For all analyses by platelet product, the platelet product type (single, double, triple, or unassigned) will be determined from the calculated platelet yield (see Section 3.3) using the following.

- If the platelet yield, rounded to the nearest tenth, is $\geq 9.3 \times 10^{11}$, then the product will be analyzed as a triple.
- Otherwise, if the platelet yield, rounded to the nearest tenth, is $\geq 6.2 \times 10^{11}$, then the product will be analyzed as a double.
- Otherwise, if the platelet yield, rounded to the nearest tenth, is $< 6.2 \times 10^{11}$, then the product will be analyzed as a single.
- Otherwise, if the procedure was not started, not completed or the platelet yield could not be determined for some other reason, as per the protocol analysis exclusion criteria, then the subject will be analyzed as “Unassigned”.

The Safety Population will include all subjects enrolled in this trial for whom at least 1 apheresis procedure is initiated. A procedure will be considered to have been initiated if a Trima procedure start date and time are present. The Safety Population will be used for all summaries except the primary and secondary endpoints and the derived apheresis related parameters.

Due to the design of the study, a given subject may be enrolled in the study on multiple occasions. These subjects may also qualify for the Safety Population more than once. If this occurs, the subjects will be analyzed separately for each enrollment.

The Full Analysis Set (FAS) will be defined separately for single, double, and triple platelet products and will not include any repeat subjects. The FAS for a given platelet product will consist of all collections that do not meet any of the exclusion criteria specified below. The FAS will be used to examine the primary and secondary endpoints and the derived apheresis related parameters.

Data points will be excluded from the FAS analysis in the following situations:

1. Inability to collect a complete unit due to:
 - a. Subject issues (inadequate access, reaction, needle abort, procedure disqualification upon Trima Accel device update of subject platelet count and hemoglobin or hematocrit).
 - b. Decision to stop procedure by subject, Investigator, nursing staff or operator.
 - c. Equipment failure or malfunction (unrecoverable system failure; plugged or malfunctioning filter[s]).
 - d. Protocol deviation.

2. Decision to stop the procedure due to a change in the subject platelet count (i.e. subject qualifies for double, however day-of platelet count is for a single platelet product and 93 single platelet products have already been collected).
3. Failure or inability to update the Trima Accel system with the actual platelet count (platelet count performed on sample taken from Trima Disposable sample pouch) AND the actual platelet count differs from the entered platelet count by more than 10%. Updating the Trima Accel system with actual platelet count from the sample pouch is standard procedure for the Trima Accel system.
4. Incomplete or incorrect collection procedure or post-collection processing due to:
 - a. Equipment failure or malfunction.
 - b. Subject issues (inadequate access, reaction, needle abort).
 - c. Unanticipated centrifuge stop during collection procedure.
 - d. Failure to follow post-collection handling procedure outlined in the Trima Operator's Manual, and supplement(s).
 - e. Subject and procedure samples are not taken as specified in protocol.
 - f. Incorrect solution added to platelets prior to storage (eg platelet additive solution).
 - g. Results of endpoint assays are not available.

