3.5 Secondary Endpoints

- Proportion of platelet units with an acceptable platelet yield for single platelet products.
- Proportion of platelet units with an acceptable platelet yield for double platelet products.
- Proportion of platelet units with an acceptable platelet yield for triple platelet products.

Acceptable platelet yield is defined as following, where the platelet yield is calculated from the formula in Section 3.3:

For single platelet products: platelet yield, rounded to the nearest tenth, $\geq 3.0 \times 10^{11}$.

For double platelet products: platelet yield, rounded to the nearest tenth, $\geq 6.2 \times 10^{11}$.

For triple platelet products: platelet yield, rounded to the nearest tenth, $\geq 9.3 \times 10^{11}$.

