Separately for single, double, and triple platelet products, the lower one-sided 95% exact binomial confidence intervals (Clopper-Pearson) will be calculated for the proportion of platelet units with an acceptable platelet yield. If the lower one-sided confidence interval is greater than 75%, then it will be concluded that the proportion of platelet units with an acceptable platelet yield is at least 75% for the given platelet product.

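### The SAP sets product type from achieved platelet yield and then tests that yield at the same cut-offs, so no analysed double or triple can fail the secondary endpoint

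*SAP*

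**What the plan says.** SAP 3.2 fixes the classification: "For all analyses by platelet product, the platelet product type (single, double, triple, or unassigned) will be determined from the calculated platelet yield". The yield is the one calculated in SAP 3.3, rounded to one decimal. At 9.3 × 10^11 or more the product is a triple; failing that, at 6.2 × 10^11 or more it is a double; below 6.2 × 10^11, "then the product will be analyzed as a single", with no lower bound. Collections without a determinable yield are unassigned.

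SAP 3.5 defines success on the same SAP 3.3 yield. The criterion that opens "For double platelet products: platelet yield, rounded to the nearest tenth" requires at least 6.2 × 10^11, and the one that opens "For triple platelet products: platelet yield, rounded to the nearest tenth" requires at least 9.3 × 10^11. Singles need at least 3.0 × 10^11.

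On the analysis set, SAP 3.2 says: "The FAS for a given platelet product will consist of all collections that do not meet any of the exclusion criteria specified below".

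The endpoint is presented as a test. SAP 3.1 says that with 93 products "16 failures or less is required to show that the proportion of platelet units with an acceptable platelet yield is at least 75" percent with 95% confidence. Protocol 15.2.2 has the same rule ("If 16 or fewer failures are observed"). SAP 3.7.3 says that if the one-sided Clopper-Pearson lower limit exceeds 75%, "it will be concluded that the proportion of platelet units with an acceptable platelet yield is at least 75" percent for that product type.

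**The concern.** For doubles and triples, the condition for entering the class is the condition for success. A class defined by a cut-off cannot be tested against that cut-off.

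The collections at issue are those that were completed, met no exclusion and still missed their target yield. The exclusions in SAP 3.2 remove incomplete, stopped, faulty or mis-entered collections; none of them covers low yield alone in a correctly run procedure. Under the SAP such a collection does not count as a failure of its own type. A triple attempt yielding 6.2 to 9.2 becomes a successful double. A double or triple attempt yielding 3.0 to 6.1 becomes a successful single. Only one below 3.0 counts as a failure, and then as a failed single.

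Yield is the sole secondary endpoint, and the rationale in the protocol synopsis names it beside leukoreduction as something the modified software must satisfy. Two of the three formal yield conclusions would carry no information about the device. The by-type means and minima do not repair this, because the same rule truncates them: no analysed double can have a rounded yield below 6.2.

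**Working it through.** **Inputs.** n = 93 per type, up to 16 failures allowed, threshold 75% (SAP 3.1, Protocol 15.1 and 15.2.2); one-sided 95% Clopper-Pearson lower limit (SAP 3.7.3); classification cut-offs (SAP 3.2); success cut-offs (SAP 3.5).

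**1. Reproduce the planned rule.** For x successes in n, the lower limit is L = the 5% quantile of Beta(x, n − x + 1).
- 16 failures: 77/93, L = 0.7505, above 0.75.
- 17 failures: 76/93, L = 0.7385, not above 0.75.

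So 16 is the correct maximum. The chance of 16 or fewer failures at a true success rate of 75% is 0.0489. The planned arithmetic is right.

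**2. Compare the two sets of cut-offs** (SAP 3.3 yield, × 10^11, rounded to the nearest tenth).

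| Type | Enters the class if (SAP 3.2) | Succeeds if (SAP 3.5) | Can fail? |
|---|---|---|---|
| Triple | ≥ 9.3 | ≥ 9.3 | No |
| Double | ≥ 6.2 and < 9.3 | ≥ 6.2 | No |
| Single | < 6.2 | ≥ 3.0 | Yes, below 3.0 |

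Applying both rules to every yield from 0.01 to 14.99 in steps of 0.01 gave 310 double values and 575 triple values with no failure among them, and 294 failing single values.

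**3. When the conclusion becomes automatic.** With no failures, L = 0.05^(1/n).
- n = 10: 0.7411
- n = 11: 0.7616
- n = 93: 0.9683

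Eleven products in a class are enough.

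**4. What the rule would do if type were the procedure run.** P(16 or fewer failures in 93), exact binomial:

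| True success rate | By procedure run | Doubles and triples under the SAP (11 or more products) |
|---|---|---|
| 70% | 0.0035 | 1 |
| 75% | 0.049 | 1 |
| 80% | 0.30 | 1 |
| 85% | 0.78 | 1 |
| 90% | 0.99 | 1 |

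**5. Illustration at the first failing count (arithmetic, not an estimate).** Assume 93 doubles run, 17 complete but short, no reclassified triples and no over-yield.
- By procedure run: 93 − 17 = 76, so 76/93, L = 73.9%, no conclusion.
- Under the SAP: the 17 leave the class, so 76/76, L = 0.05^(1/76) = 96.1%, conclusion drawn.

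**6. Effect on singles, under the SAP's all-collections analysis set.** Start from 76/93 (L = 73.9%, does not pass) and add short doubles that yielded at least 3.0.
- 4 added: 80/97, L = 74.9%, does not pass.
- 5 added: 81/98, L = 75.1%, passes.
- All 17 from step 5 added: 93/110, L = 77.7%, passes.

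A reclassified collection below 3.0 would instead lower the singles result.

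**The case against.** The identity itself has no answer in the documents, but several points bear on its weight.

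- **Yield is secondary.** The stated objective is leukoreduction, and SAP 1.0 describes the analyses as descriptive. That is true, but SAP 3.7.3 still draws a formal conclusion for each type, and that conclusion is what fails.
- **The cut-offs are laboratory minimums for splitting** (footnotes in Protocol 7.2 and SAP 3.7.3). This is a fair reason to label products by what can be made from them. It does not make the label testable against its own definition.
- **The decision may seldom change.** With a true success rate of 90%, the by-procedure rule passes with probability 0.99, so a reversal is unlikely unless shortfalls exceed roughly 10%. This stands: no shortfall rate is given. The reported proportion would nevertheless be fixed at 100%.
- **The singles arithmetic depends on the SAP's analysis set.** Protocol 15.3 limits each set to the first 93 eligible collections, under which denominators of 97, 98 or 110 cannot arise. This also stands, and step 6 is conditional on the SAP text. It does not touch doubles and triples.
- **The listings contain all eCRF data.** Shortfalls could be reconstructed if the procedure run is recorded there, but that does not replace the planned test.

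The protocol does not expressly define type for analysis. It does qualify subjects for a procedure from the platelet count (Protocol 10.3 and 15.4), before any yield exists, and it contains no reassignment by yield. Its 16-failure allowance makes sense for doubles and triples only if they can fail.

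**Conclusion.** The concern holds, with high confidence, and must be fixed. Under SAP 3.2 and 3.5 the yield success rate for doubles and triples is 100% with certainty, and the 75% conclusion follows automatically from 11 products upward, whatever the device's yield performance. The intended error rate of about 5% at a true rate of 75% does not exist for these two types. This rests only on the SAP's own definitions. The by-procedure probabilities also assume 93 products per type and independent binomial outcomes. How often collections would be reclassified, and so how often a conclusion would reverse, cannot be determined from the documents.

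**What to change.** In SAP 3.2 and 3.5, for the secondary yield endpoint, define type as the single, double or triple procedure run on the device after the platelet-count update. Count a completed, non-excluded collection that misses its type's cut-off as a failure of that type. Show achieved-yield class only as a descriptive cross-tabulation against procedure run. State that the yield denominators and by-type yield summaries follow the procedure run, since they may then differ from those used for residual WBC.

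No change to the WBC limits is proposed. The SAP should state whether the limit applied to a product follows the procedure run or the units actually obtainable, consistent with the objective's per-transfusable-unit requirement.

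The cost is SAP wording, one derived variable, one cross-tabulation and yield tables produced on the new variable. The sponsor must confirm that the procedure run is captured in the device procedure details recorded under Protocol 10.2.2; if it is not, it must be retrieved from site source documents. Reported yield success for doubles and triples may fall below 100%, and the 75% conclusion could then fail.
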